We anticipate reaching our recruitment goal within 9 months of beginning enrollment. In prior trials in Philadelphia with sexual and gender minorities in this age group, we have found that over 40% of individuals who clicked on our online ads through social media screen were eligible. Of those, 80% provided full contact information and about 40% scheduled and attended an in-person enrollment visit. We expect most (~85%) will consent and enroll in the trial. Thus, for the proposed study, we expect to screen about 550 individuals to conduct full eligibility evaluations with approximately 70 EASM inperson over the 9-month period, and consent and randomize 64 for our study. Based on these estimates, we will plan to randomize 5-7 participants per month over the course of 9 months. Recruitment contingency plan: Today, geosocial networking apps and other social media are the primary means through which to recruit EASM, and thus are an ideal environment to engage these populations for research. Our team has worked with the major social media platforms (Facebook, Twitter, Instagram) to enroll participants for more than a decade. Nevertheless, we recognize the ephemeral nature of technology and shifting climate in the popularity of various social media platforms (e.g., emergence of Snapchat, WhatsApp, Telegram, and TikTok as alternate social media avenues). As our team has done for over a decade, we will continually anticipate how platforms have changed to adjust our recruitment and meet our recruitment goals. This will include ongoing conversations with our existing platforms

collaborators, as well as establishing connections with emerging platforms. If necessary, we will also leverage our connections in the Philadelphia community and conduct in-person recruitment and word of mouth referral. Our advertising budget is appropriately robust to account for the true costs for advertising on these platforms and will work with apps/social media to ensure that we are able to meet our recruitment goals within budget.

2. Key Inclusion Criteria:

(1) identify as a sexual minority; (2) live in the Philadelphia Metropolitan Area; (3) report suicide ideation in the prior month; (4) be aged 18-24 years; (5) have daily smartphone access; and (6) not plan to move out of the region for the next 12 months.

3. Key Exclusion Criteria:

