Although iREACH was developed to reduce HIV risk behavior in sexual minority youth and not intended to address mental health or suicide risk, it includes therapeutic targets for factors that predict suicidal ideation and behavior among EASM. In Aim 1, we will use the ADAPT-ITT framework to develop a complementary approach STARS to reduce suicide ideation among at-risk EASM. STARS will embed components of the Safety Plan Intervention as well as modules focused on promoting coping with discrimination, social support, and positive affect. We will pilot test STARS using a Type 1 Effectiveness-Implementation Hybrid Design in a racially/ethnically diverse sample of 64 EASM who report past-month suicidal ideation. We will recruit EASM through social media and invite them to an in-person screening and consent session. Eligible participants will complete a Safety Planning Intervention with a licensed clinician, given the high-risk nature of the sample. They then will be randomized to the control condition (CC, n = 32) or STARS (n = 32). We will follow participants for 6 months, with evaluations at 2, 4, and 6 months. Primary outcomes will be preliminary efficacy outcomes of suicidal ideation and behavior and hypothesized mechanisms of change (improved coping with discrimination, social support, positive affect). Secondary outcomes will be RE-AIM framework indicators (reach, adoption, implementation, maintenance). *Define the duration of the study and describe how the aims of the study can be met within the specified duration of the study.*

Study duration

The study is funded for approximately 3 years. Once consented, participants will be active in the study for 6 months, as described in the "Design" section.

METHODS:

1. Measures:

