Primary outcome variable(s): The primary outcomes are cognitive in nature and include: 1) Name: Suicidal Ideation and Behavior a. Type: Primary b. Timeframe: Baseline, 2 months, 4 months, 6 months c. Brief description: The Columbia-Suicide Severity Rating Scale (C-SSRS) is an interview-rated measure that will be completed by a blind independent evaluator. The C-SSRS includes three subscales, namely suicidal ideation, intensity of ideation, and suicidal behavior. The measure has strong psychometric properties, including inter-rater reliability and internal consistency. The suicidal behavior and the suicidal ideation subscales have been shown to predict future suicidal behavior. The following outcomes are treated as mechanisms of intervention action: 2) Name: Social Support a. Type: Secondary b. Timeframe: Baseline, 2 months, 4 months, 6 months c. Brief Description: Support from parents and friends, respectively, will be measured through a five-item emotional support scale developed, with items rated on a 5-point scale. The measure has strong convergent and divergent validity, as well as a strong test-retest reliability and internal consistency.

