exports will be converted into an SPSS working file. Data will be stored in a physically secure environment, and all data files will have encryption and strong password protection. Access to data will be on a role-based standard; only those study staff that require access to identifying data to complete their study-related roles will be allowed access, as described above. All study staff will be trained in security and confidentiality procedures, and will sign a confidentiality agreement before receiving access to any participant data. Contact information used to confirm participation will be held in a password-protected database on a secure university server, accessible only by study staff. This contact information will be held separately from baseline and follow-up survey data, which will contain only the participants study identification number. The database will be backed up to a hard drive housed in another location, also accessible only by study staff. The contact information (name, email address and phone number) in the database will be destroyed at the end of the study, and will never be associated with the study data collected. Norton Clean-Sweep software will be used to delete the database file from *the secure server and the back-up file(s) from the separate hard drive*.

7. Subject Follow-up:

Self-completed study assessments are conducted virtually (REDCap Survey) every two months across the intervention and attention-control follow-up time points, with a total follow-up period of 6 months. Phone follow-up clinical interviews are conducted at 2, 4 and 6 month timepoints.

Retention: Upon study entry, we will make all efforts to retain consented participants. Our study retention plan draws on previously successful retention protocols to achieve at least an 80% retention rate. Our experience has shown that successful retention has several key elements. First, it is critical to obtain accurate follow-up contact information. We will use best practices to retain participants (e.g., comprehensive locator information that includes participants' cell phone number, e-mail, Facebook and/or Twitter username, and contact information for 2 peers who could help us contact them), while being sensitive to undue disclosure of EASM participating in the study. We also have a pre-planned schedule of follow-ups that consists of a variety of follow-up methods.

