any questions on the surveys that they are uncomfortable answering. They will also be informed about the limits of confidentiality as it relates to imminent suicide risk or risk of imminent harm to others and the need to enact emergency procedures to ensure their safety and the safety of others. Psychological distress is a potential risk to EASM during the completion of the interviews or surveys, reading the intervention content, creating a safety plan at the baseline evaluation, and during the peer mentor session. We will provide EASM with information to allow them to contact the study team at any time if they experience psychological distress related to participation in the study. In addition, at the time of study enrollment, we will solicit up to 3 personal contacts of study participants to call in the event that a participant is in a psychiatric crisis but is unreachable for some reason. We will inform participants about why we are collecting information for these emergency contacts, remind them that providing this information is optional, and describe to them the procedure for calling these contacts in the event of an emergency. We will clarify with participants what information will and will not be shared with the emergency contacts. For instance, we will share that we are calling from the Penn Health System and are worried about the participant and want to make sure that he is okay but are unable to reach him. We will then ask the emergency contact whether they have been in touch with the participant and could help us to locate him. We will not reveal the name of the research study or provide any information that has the capacity to unintentionally reveal the sexual or gender orientation of the participant. We will share with participants that they have permission to revoke consent for us to contact these emergency contacts at any time, and to just let us know that preference verbally or in writing. [name] has used this strategy successfully for working with individuals who are living with HIV and who reported past month suicidal ideation. In the prior studies that used this approach, most participants provided at least one study contact, though we never needed to call any of the emergency contacts because of the strong rapport that we established with participants during the baseline assessment and other research procedures. If psychological distress is apparent during a peer mentor session or other study contact, our licensed clinicians will be available to talk with the participant. Our licensed clinicians are familiar with the emergency management protocols at Penn and throughout the city of Philadelphia. If needed, we will participants in immediate crisis to the Mobile Crisis Response Team which is available 24 hours a day, 7 days a week. This Mobile Crisis Team is a service offered through the city of Philadelphia that can drive to patients/participants home to help transport them to the psychiatric emergency department, or can de-escalate the risk at home. In addition, participants will be provided with the number for the National Suicide Prevention Lifeline and the licensed study clinician at the time of consent. Some participants may opt to include the number for the Mobile Crisis Response Team, the National Suicide Prevention Lifeline, or the number of the licensed study clinician to their Safety Plan, but this will not be required. Research staff will receive training in crisis assessment and management procedures to assist with the management of suicidal and/or homicidal ideation, or child physical/sexual abuse. We will notify participants when we must engage in mandatory reporting during the consent process and when the participant decides to share a reportable event with study staff. At the beginning of any phone contact with participants, the researcher will first ask the participant to identify their physical location. This will ensure that if deployment of emergency services is required, we know how to reach the participant in crisis. Unintended disclosure is also a potential risk. Participants will be instructed at different moments during the study (e.g., screening, baseline, follow-up) of steps they can take to further protect their privacy (e.g., clear browser history; avoid saving username/password in browser; logging out every time; using the app in private; using a screen lock on their phones, if parents allow).

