management procedures to handle both suicidal crises, as well as reports of homicidal ideation and risk of child abuse. We will use established protocols from our prior studies conducted with men who have sex with men (MSM) and with individuals at high risk for suicide to guide research staff in responding to crisis or harm situations, including attempting to contact the participant to assess risk level and provide appropriate follow-up (e.g., crisis hotline, safety check, suicide hotline). Staff will be required to contact our full-time clinical counselor ([name]) or clinician ([name]) to manage situations of higher risk. Risk of coercion. Using online recruitment methods where the intervention is not pitched by a recruiter minimizes the risk of potential coercion. Instead, EASM will be able to choose and click on the recruitment advertisement and decide if they wish to learn more or not. Similarly, staff will be trained to discuss all elements of the consent process with potential participants. Consent documents will fully explain the study procedures, potential risks, and potential benefits. Participants will also be reminded that the study participation is voluntary and that refusing to participate in the study or withdrawing from the study is an option at any time. Informed consent documents will be available in English and have grade 5 reading level. Adequacy of Protection against Risks a. Recruitment and Informed Consent We will recruit subjects through the placement of banner advertisements on Facebook and other social media outlets. For those who click on the ad, they will be taken to a page describing the nature of the study: if they then click on interested in participating they will be asked to complete an interest form which will be used by study staff to schedule an in-person visit. During the in-person visit, eligible participants will be given a written informed consent document. We will employ several strategies to offset risks of loss of confidentiality related to participating in our trial. First, we will petition a Certificate of Confidentiality from the Department of Health and Human Services (an explanation will follow indicating that in studies thus covered the researchers have not been forced to release any research data from participants, even under a court order or subpoena). Participants who experience distress during the survey can access our list of community referrals, which can be viewed on our study's application, or contact the research team directly (toll-free number is embedded into the About Us section of the application). Participants can contact study staff to get referrals to local services, and should participants report or display signs of distress during the teleconference interactions they will be asked to speak with a clinician who is a member of the research team. Any unexpected adverse events will be immediately reported to the IRB, and all study activities will halt pending IRB review and recommendations. It will be made clear to all participants in the consent forms that participation in the pilot RCT will not affect their access to any services in their community. The consent document will make it clear that participants can attend any services in their local area and that they do not have to participate in the trial to access services, nor do they have to reveal their participation in the trial to anyone at these agencies. Participants who chose not to participate in the trial will still be able to access the list of local LGBT resources. Participants addresses and any other identifying information will be kept in a separate, password-protected file to avoid risk of identification. All stored data will be kept in a locked room at the University of Pennsylvania. Electronic data will be maintained in a secure server. Access to the data will be located in a folder with restrictions (i.e., may be accessed only by study team members). Access to data will be on a role-based standard; only those study staff that require access to identifying data to complete their study-related roles will be allowed access, as described above. All study staff will be trained in security and confidentiality procedures, and will sign a confidentiality agreement before receiving access to any participant data. We will also develop procedures to minimize indirect disclosure that a participant is enrolled in a study focused on EASMs suicide vulnerability. For each mode of re-contact information,

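### The automatic halt after an unexpected adverse event has no carve-out, so read literally it also pauses the 2-, 4- and 6-month suicidality interviews

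*Combined protocol and SAP*

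**What the plan says.** The halt rule is in RISK/BENEFIT ASSESSMENT, under a. Recruitment and Informed Consent: "Any unexpected adverse events will be immediately reported to the IRB, and all study activities will halt pending IRB review and recommendations". The trigger carries no condition of seriousness or relatedness, *unexpected* is not defined, and no activity is excepted.

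The activities that matter here are described elsewhere:

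- METHODS, 1. Measures, on the primary outcome: "The Columbia-Suicide Severity Rating Scale (C-SSRS) is an interview-rated measure that will be completed by a blind independent evaluator". It is scheduled at baseline and at 2, 4 and 6 months.
- METHODS, 7. Subject Follow-up: "Phone follow-up clinical interviews are conducted at 2, 4 and 6 month timepoints". The same section sets the retention target: "Our study retention plan draws on previously successful retention protocols to achieve at least an 80% retention rate".
- Key Inclusion Criteria: participants must "report suicide ideation in the prior month".
- STUDY DESIGN, Design, on what happens before randomisation: "Eligible participants will complete a Safety Planning Intervention with a licensed clinician, given the high-risk nature of the sample".
- RISK/BENEFIT ASSESSMENT, 1. Risks: "If psychological distress is apparent during a peer mentor session or other study contact, our licensed clinicians will be available".

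**The concern.** Stopping enrolment, randomisation and intervention delivery while the IRB looks at an unexpected event is a sensible protective default and is not criticised. The difficulty is that the same sentence also covers outcome and risk assessment.

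Everyone in the trial enters with recent ideation, and the protocol itself calls the sample high-risk. Controls complete safety planning before randomisation and have neither the app nor a peer mentor. After baseline, their main scheduled contacts are the 2-, 4- and 6-month interviews and surveys. Contact details are also to be updated quarterly, but that is not a risk assessment. Clinician availability under 1. Risks depends on distress showing itself during some study contact, so fewer contacts mean fewer occasions for it to be noticed. A literal halt would therefore postpone scheduled questioning about suicidality just after a safety signal.

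There is a smaller cost to the data. The Statistical Analysis section codes visit nominally (pre/post, 0 to 3, or categorical), and I found no visit windows. A delayed interview would be analysed as if it were on time.

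**Working it through.** **Text check.** I read the halt sentence against Measures, Subject Follow-up, Risks, Recruitment and Informed Consent, Protections against Risk, Data and Safety Monitoring (including Reporting Adverse Events) and Consent Process.

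- Reporting Adverse Events says who must be told about an event. It neither narrows the halt nor keeps any assessment running.
- The monitoring board text does not mention the halt.
- Risks and Recruitment and Informed Consent describe crisis response, including staff reaching out to a participant to gauge risk. Neither says what continues during a halt.
- Subject Follow-up does not name the C-SSRS. That its phone interviews are the C-SSRS interviews is an inference from the matching format (interview) and schedule (2, 4 and 6 months).

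So no exemption is stated.

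**Size, for illustration.** The plan gives no figure for a halt, so there is none to reproduce.

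Inputs from the protocol: 64 participants, 9 months of accrual, three follow-up interviews each, and an 80% retention target. Assumptions: even accrual, 80% retention at every visit in the second scenario, a trial-wide halt of 1, 2 or 4 weeks lying wholly within follow-up, and no knock-on shift from paused randomisation.

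1. Accrual rate: 64/9 = 7.1 a month. The Accrual section says "we will plan to randomize 5-7 participants per month over the course of 9 months"; 5 × 9 = 45 and 7 × 9 = 63, so 7.1 sits at the top of that range.
2. Total interviews: 64 × 3 = 192 at full retention; 192 × 0.8 = 153.6, about 154, at 80%.
3. Calendar: 2-month interviews fall in months 2-11, 4-month interviews in months 4-13 and 6-month interviews in months 6-15. One visit stream runs in months 2-4 and 13-15, two in months 4-6 and 11-13, and three in months 6-11.
4. Monthly load: lowest 7.1 (one stream), highest 3 × 7.1 = 21.3 (three streams). At 80%: 5.7 and 17.1. Check: 7.1 × 4 months + 14.2 × 4 months + 21.3 × 5 months gives 192 (unrounded rates).
5. Interviews falling due in a halt = monthly load × halt length, with 1, 2 and 4 weeks = 0.23, 0.46 and 0.92 months.

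| Halt | Full retention (of 192) | 80% retention (of 154) | Share |
|---|---|---|---|
| 1 week | 1.6 to 4.9 | 1.3 to 3.9 | 0.9% to 2.6% |
| 2 weeks | 3.3 to 9.8 | 2.6 to 7.9 | 1.7% to 5.1% |
| 4 weeks | 6.5 to 19.6 | 5.2 to 15.7 | 3.4% to 10.2% |

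With 1:1 allocation about half of these are controls: for 4 weeks, 3.3 to 9.8 at full retention.

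**The case against.** The case for leaving the sentence alone has several parts.

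*Assessments are themselves a named source of risk.* Risks lists distress from interviews and surveys, and possible disclosure through study emails and online surveys. An unexpected event could arise from an assessment, and the IRB can already release activities once it has reviewed. This stands in part. It justifies an exception for assessment-related events and an IRB override, but not a default stop to every interview after every unexpected event.

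*The literal reading is too strict.* A reader might infer that the halt cuts off all safety contact. The documents do not support that: clinician response, staff outreach and external crisis services are described separately and may reasonably be read as continuing. The C-SSRS is also presented as outcome measurement, not as the safety-monitoring system. That narrows the concern to scheduled assessment.

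*The trigger may be rare.* A reader might infer frequent halts in so high-risk a sample. With *unexpected* undefined, worsening ideation might well be classed as expected here, so no frequency can be claimed. Nor does the text say outright that a halt is trial-wide, though its wording reads that way.

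*A simple carve-out could do harm.* Stopping the whole STARS app would also close the referral list and the toll-free number held there (Recruitment and Informed Consent), and the consent copy and dis-enrolment route (Consent Process). Measuring STARS participants on schedule while delivery is paused also means measuring them after less exposure. Both points stand and shape the fix.

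**Conclusion.** The point holds in a limited form. The stated rule is broader than it needs to be: followed as written, it pauses scheduled suicidality interviews in people enrolled for recent ideation, and no other section exempts them. On the assumptions above, a halt of 1, 2 or 4 weeks would delay about 2-5, 3-10 or 7-20 of 192 interviews, or about 1-4, 3-8 or 5-16 of 154 at 80% retention.

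These figures rest on even accrual, assumed halt lengths and a trial-wide halt. The link between the phone interviews and the C-SSRS is also inferred.

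Two further inferences should be resisted. A reader might conclude that outcome data would be lost, but the interviews are delayed and not necessarily missed. A reader might also conclude that the current rule biases the treatment comparison, but the interview delay falls on both arms alike and delivery pauses with it, so no between-arm bias is claimed. Nothing shows that the team intends to stop safety contact. This is a cheap improvement to consider, held with medium confidence.

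**What to change.** Keep the automatic halt for new enrolment, randomisation, peer mentor sessions and the STARS intervention modules. After the halt sentence in Recruitment and Informed Consent, add:

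> *Scheduled C-SSRS interviews and follow-up surveys continue in both arms during the halt unless the event appears related to an assessment procedure or the IRB directs otherwise. Clinician risk response and safety contacts, and access to the application's referral list, contact number, consent form and dis-enrolment function, also continue unless the IRB directs otherwise.*

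Two sentences are used so that an assessment-related event pauses the assessments without pausing risk response. Add a cross-reference under Reporting Adverse Events and leave its reporting duty as it is. Record the start and end dates of any halt and report them with the results.

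The cost is a short IRB amendment, with no added participants, visits or staff. There are two small downsides. Some research contact continues during the pause. STARS participants assessed during a halt will have had slightly less intervention exposure, which could slightly dilute the comparison; the recorded halt dates let readers judge this.
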